1.0 PROTOCOL SYNOPSIS

TITLE OF STUDY	AN IMAGING AND BIOMARKER EVALUATION OF HEPATIC STIFFNESS IN CHILDREN ENROLLED IN THE FONTAN UDENAFIL EXERCISE LONGITUDINAL STUDY
PHASE	Open Label Extension
STUDY OBJECTIVE	Determine scope of hepatic stiffness in Fontan patients by ultrasound and magnetic resonance imaging elastography and evaluate the efficacy of udenafil in reducing liver stiffness.
SIGNIFICANCE	Study will obtain necessary and broad information regarding hepatic stiffness in Fontan patients and will be the first to evaluate a potentially efficacious treatment to reduce liver stiffness.
STUDY DESIGN	Prospective cohort study integrated with the Fontan Udenafil Exercise Longitudinal (FUEL) clinical trial
PLANNED SAMPLE SIZE	50-150 Subjects
KEY SUBJECT SELECTION CRITERIA	
Inclusion Criteria:
 
1. Enrollment in FUEL Extension Trial2. Informed assent from subject, informed consent from parent/legal guardian as appropriate 
Exclusion Criteria:
 
1. Non-enrollment in the FUEL Extension Trial2. Subjects with contra-indications for MRI (these subjects will be excluded from the MRI component of this study)3. Other exclusionary criteria will match those used for the FUEL Extension Trial
TREATMENT	One year of udenafil treatment (87.5 mg twice daily)
PRIMARY AIM	Define the range of liver stiffness in those who have had the surgical creation of a total cavopulmonary connection.

SECONDARY AIMS:	
• Determine the impact of udenafil treatment on liver stiffness in a large cross-section of adolescents who have undergone total cavopulmonary connection.• Determine the relationship between clinical outcomes and liver stiffness.• Assess the association between biomarkers of both heart failure and liver fibrosis and liver stiffness.
EFFICACY PARAMETERS	Reduction in liver stiffness after initiating udenafil therapy adolescents with Fontan physiology.
EFFICACY ASSESSMENTS	Efficacy will be assessed at FUEL-OLE initiation and conclusion.
EFFICACY ENDPOINTS	Absolute liver stiffness as measured by ultrasound (and MR) and change in liver stiffness.
SAFETY PARAMETERS	As this study has no active intervention, there are no specific safety measures beyond FUEL-OLE protocols.
SAFETY ASSESSMENTS	As this study has no active intervention, there are no specific safety assessments beyond FUEL-OLE protocols.
STATISTICAL ANALYSES	
Analysis Populations: All individuals enrolling in FUEL-OLE will be recruited for enrollment in the FALD study. At completion of FUEL-OLE, once FUEL assignments are unblended (udenafil or placebo), the cohort will be stratified into udenafil naïve vs. udenafil continuation groups. Analysis will be done both on an intent-to-treat and a per-protocol basis.
 
General Statistical Methods: This is prospective observational study of liver stiffness in Fontan patients. Absolute liver stiffness and association of degree of stiffness liver biomarkers will be assessed for the entire cohort. Change in liver stiffness over the 12-month FUEL-OLE duration will be assessed both for the overall cohort and after stratification into udenafil naïve vs. udenafil continuation groups.

FINAL DATE	December 11, 2017

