3.2 Rationale for the Study and Study Outcomes

3.2.1 Study Rationale

While there have been many small studies that have used SWE to evaluate the degree of liver stiffness in patients who have undergone TCPC, there has not been a large-scale evaluation that defines “normal” in this population or seeks to correlate liver stiffness with functional outcome. Similarly, the impact of treatment with pulmonary vasodilators, medications that should lower systemic venous pressure, has not been evaluated. The FUEL Extension trial presents a unique opportunity to measure liver stiffness in those with TCPC, to evaluate the impact of udenafil on liver stiffness, to correlate liver stiffness with functional outcomes, and to gain valuable insight into the relationship between liver stiffness and biomarkers of heart failure and fibrosis.

[figure not shown]

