4.2 Primary Aim and Hypothesis

Primary Aim: Define the range of liver stiffness in those who have had the surgical creation of a total cavopulmonary connection.

Hypothesis: Following total cavopulmonary connection, children with single ventricle congenital heart disease will have elevated measures of liver stiffness.

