5.0 STUDY DESIGN

This is an open-label extension study that integrates with the FUEL Extension Trial. FUEL-enrolled patients will have been randomized and double-blinded to either placebo or udenafil, and all patients entering the FUEL Extension trial will be placed on udenafil therapy. Therefore, approximately 50% of patients eligible to be enrolled in our study will be udenafil-naïve (U-) and 50% will have already completed 6-months of therapy (U+). As a part of FUEL-OLE, each participant will receive one year of udenafil treatment (87.5 mg twice daily). Both the U- cohort and the U+ cohort will have liver stiffness measured by ultrasound and MR elastography (where available), as described above. Thus, the U- subjects will have elastography measurements pre-udenafil and after 1 year of treatment. This will determine the impact of udenafil therapy on liver stiffness. Additionally, the U+ cohort from FUEL will allow us to determine if potential benefits of udenafil therapy are sustained over time by comparing measurements after 6 (baseline entry into our study) and 18 months of therapy (after 1-year of our study). The study visits are as follows:

1. Baseline visit: during the baseline visit, subjects will undergo ultrasound SWE and, if available at their center, magnetic resonance elastography. These will be coordinated with FUEL extension testing to ensure that the primary study is not interrupted. The additional blood work for this protocol will be obtained at the same time as the blood work for the FUEL extension study.
2. Follow-up visit: during the follow-up visit, subjects will undergo ultrasound SWE and, if available at their center, magnetic resonance elastography. These will be coordinated with FUEL extension testing to ensure that the primary study is not interrupted. The additional blood work for this protocol will be obtained at the same time as the blood work for the FUEL extension study.

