9.4.2 Primary Outcome

The absolute stiffness by SWE and by MR elastography will be reported using descriptive statistics as appropriate.

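### Does the primary description of liver stiffness need a named visit and a separate udenafil-naive range?

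*Combined protocol and SAP*

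**What the plan says.** The primary aim in section 4.2 is to "Define the range of liver stiffness in those who have had the surgical creation of a total cavopulmonary connection", with the hypothesis that stiffness is elevated. The whole primary analysis, in section 9.4.2, is one sentence: "The absolute stiffness by SWE and by MR elastography will be reported using descriptive statistics as appropriate". Section 8.1 likewise names no visit or group.

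The synopsis adds a population: "Absolute liver stiffness and association of degree of stiffness liver biomarkers will be assessed for the entire cohort". Its next sentence treats change differently: change over the 12 months "will be assessed both for the overall cohort and after stratification into udenafil" naive and continuation groups. The synopsis also lists the efficacy endpoints as "Absolute liver stiffness as measured by ultrasound (and MR) and change in liver stiffness", and on timing it says "Efficacy will be assessed at FUEL-OLE initiation and conclusion".

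Section 5.0 sets the treatment history. About half the eligible subjects are udenafil-naive (U-) at entry and half have had six months of drug in the parent trial (U+); all then receive it for a year. Section 9.3 stratifies the cohort into these two groups after unblinding. The first analysis under secondary outcome 1 in section 9.4.3 compares U+ with U- on baseline stiffness. Section 9.1 leaves data conventions and detailed procedures to a SAP that must be final before the database is locked.

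**The concern.** Section 3.2.1 justifies the study on the ground that "there has not been a large-scale evaluation that defines" what is normal after TCPC. A reader may therefore take the primary range as a reference for Fontan patients in general, most of whom would not be on udenafil. Secondary Aim 1 hypothesises that the drug lowers stiffness. If it does, a whole-cohort range at baseline is pulled down by the pretreated half, and one at 12 months is pulled down throughout. Only the U- baseline scans are untreated.

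The synopsis wording adds to the worry, because it promises stratification for change and not for absolute stiffness. At stake would be a reference range set too low and not labelled as partly treated, with the visit and group for the primary result chosen after the data were seen.

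**Working it through.** **1. Inputs.** From section 9.2: mean 2.08 m/s and SD 0.24 for shear wave speed, and a pre-TCPC mean of 1.18. From section 6.1: 50-150 subjects, so 25-75 per group at an even split. The effect *e* already present in U+ at baseline is not given; 0%, 5% and 10% are assumptions. (The 10% in section 9.2 is a 12-month reduction used for sample size.)

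**2. The plan's own figure.** The primary description has no sample size. The 12 per group for secondary outcome 1 reproduces as (0.24 × (1.960 + 1.036) / 0.208)² = 11.95, rounded up to 12, if 0.24 is taken as the known SD of the change. It has no bearing on this point.

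**3. Untreated share of a whole-cohort summary.** About 50% at baseline and about 0% at 12 months.

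**4. Effect of pooling at baseline.** The pooled distribution is 0.5·N(2.08, 0.24) + 0.5·N(2.08(1 − e), 0.24). Its mean is 2.08(1 − e/2) and its SD is √(0.24² + 0.25(2.08e)²). The 2.5th and 97.5th percentiles are solved numerically.

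| e | Pooled mean | Pooled SD | Central 95% range | Untreated patients above the pooled upper limit |
|---|---|---|---|---|
| 0% | 2.080 | 0.240 | 1.610-2.550 | 2.5% |
| 5% | 2.028 | 0.246 | 1.547-2.509 | 3.7% |
| 10% | 1.976 | 0.262 | 1.465-2.487 | 4.5% |

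At 10% the lower limit moves by 1.610 − 1.465 = 0.145 m/s and the upper by 2.550 − 2.487 = 0.063.

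**5. The primary hypothesis.** At 10% the pooled mean exceeds the pre-TCPC mean by 1.976 − 1.18 = 0.796 m/s. With all subjects shifted by 10% at 12 months the mean is 2.08 × 0.9 = 1.872, still 0.692 above it. Elevated stiffness is concluded either way.

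**6. What the planned U+ versus U- comparison shows.** The effect that would distort the pooled range is the difference tested in section 9.4.3. At 10% that is 0.208 m/s. With 25 per group its standard error is 0.24 × √(2/25) = 0.068, so the difference is about 3.1 standard errors. At 5% (0.104 m/s) it is about 1.5 standard errors with 25 per group, and with 75 per group 0.104 / (0.24 × √(2/75)) = 0.104 / 0.039, about 2.7. If the SD were 0.48 (assumption), these ratios halve.

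**7. What a separate U- range would resolve.** The normal-theory half-width for a 2.5th or 97.5th percentile is 1.96 × SD × √(1/n + 1.96²/(2(n − 1))). With SD 0.24 it is 0.163 at n = 25 and 0.093 at n = 75. At n = 25 it exceeds both 10% shifts. The lower shift is resolved only from about n = 32, and the upper only from about n = 164, beyond any planned group. With SD 0.48 the half-widths are 0.326 and 0.186 against shifts of about 0.13 and 0.08, so neither is resolved. Without normality, a two-sided 95% interval for the 2.5th percentile has a finite lower limit only if 0.975ⁿ ≤ 0.025, that is n ≥ 146.

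**The case for a change.** The best case for a change is that the visit and population of a primary outcome belong in the protocol. The one text that assigns a population says entire cohort, while the next sentence stratifies change only, so a SAP author could fairly read this as an instruction to pool. The visit matters more than the mix. If the range were taken at 12 months with a 10% effect in everyone and no other change over time, it would be 1.40-2.34 m/s. About 14% of untreated patients would lie above that upper limit, since (2.342 − 2.08)/0.24 = 1.09. Naming the baseline visit and splitting one table would cost a few words.

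It stands that no visit is named and that the synopsis pools absolute stiffness. The rest is weaker. Stating a result for the entire cohort does not exclude a by-group table, and section 9.3 stratifies the cohort without limiting that to change. The synopsis gives both the start and the end of the extension as assessment times, so reporting each visit separately is the natural reading. The primary outcome carries no test, so the choice of visit cannot turn a null result into a positive one. Prior treatment is the central feature of section 5.0, and nothing suggests a report would hide it.

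**Conclusion.** No change to the plan follows. This is missing detail that the SAP can supply, not a wrong analysis. The aim and the primary assessment do not ask for untreated patients, so a whole-cohort summary answers the question as written. For a reader who wants the untreated range, the U- baseline values are already collected and compared with U+ under section 9.4.3.

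The possible distortion at baseline runs from nothing to a 5% lower mean (2.080 to 1.976 m/s), and the conclusion that stiffness is elevated holds throughout. These figures assume an even split, normality, the plan's SD of 0.24 and an effect of 0-10% in U+ at six months. The SD comes from scans six months after surgery, apparently in few children (section 3.2.2.1 mentions five late returns), whereas this cohort is aged 12-19. The full shift is itself uncertain: section 11.1 plans baseline imaging before that day's study drug, so U+ subjects have prior exposure without any stated dosing status at the scan. At the planned group sizes a separate naive range would mostly serve as a label, because its limits are too imprecise to show most of the shifts in question.

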2.0 LIST OF ABBREVIATIONS

Abbreviation or Term	Definition/Explanation
ARFI	Acoustic Radiation Force Impulses
BNP	Brain natriuretic peptide
CAE	Common adverse event
CRF	Case report form
CHD	Congenital Heart Disease
DCC	Data coordinating center
DMS	Data Management System
EDC	Electronic data capture
ELF	Enhanced Liver Fibrosis
ELISA	Enzyme linked immunosorbent assay
FALD	Fontan-associated Liver Disease
FDA	Food and drug administration
FUEL	Fontan Udenafil Exercise Longitudinal Trial
HA	Hyaluronic Acid
ID	Identification
IRB	Institutional Review Board
MRI	Magnetic Resonance Imaging
NHLBI	National Heart, Lung, and Blood Institute
PAT	Pulse amplitude tonometry
PDE5i	Phosphodiesterase type 5 inhibitor
PHN	Pediatric Heart Network
PI	Principal investigator
PIIINP	Amino-terminal propeptide of type III collagen
RCT	Randomized control trial
ROC	Receiver operating characteristic
RT	Reverse Transcription
SAP	Statistical Analysis Plan
SWE	Shear Wave Elastography
SAE	Serious adverse event

TCPC	Total Cavo-pulmonary Connection
TIMP-1	Tissue inhibitor of metalloproteinase-1
UMPL	University of Michigan Pathology Laboratory
US	Ultrasound

[figure not shown]
3.0 BACKGROUND INFORMATION AND RATIONALE

3.1 Discussion of Hepatic fibrosis and FUEL Trial Extension Study

3.1.1 FALD

Fontan-associated liver disease (FALD) is defined as abnormalities in liver structure and function resulting from the abnormal circulation created by the total cavopulmonary connection (TCPC) and not related to any other process (1). FALD is increasingly recognized as one of the most common complications of the TCPC (2, 3) and one which is universally present in patients with TCPC physiology (8-11). After the Fontan operation, blood from the inferior and superior vena cava are routed directly to the pulmonary arteries bypassing the heart (Figure 1). In this circulation, blood is not “pumped” through the lungs but is “pushed” through by chronic elevation of the central venous pressure. It is postulated that the Fontan’s elevated, non-phasic systemic venous pressure results in obligate chronic hepatic venous hypertension and congestion that is likely an important driver of hepatic fibrosis. As part of the injury response, activated myofibroblasts deposit excess extracellular matrix in the perisinusoidal space, a process which, if it persists, can lead to increased hepatocellular injury, progressive fibrosis, organ dysfunction, and, ultimately, to cirrhosis and hepatic failure. The congestion and fibrosis result in a wide spectrum of liver disease, including synthetic dysfunction, ascites, portal hypertension, cirrhosis, and hepatocellular carcinoma, and may culminate in fulminant liver failure. The severity of liver fibrosis is known to increase with time after TCPC and occurs in the absence of any other identifiable etiology of chronic liver disease.

Figure 1: Description of Fontan Associated Liver Disease

3.1.2 Characterization of FALD

A roadblock to understanding and treating FALD is the lack of an established, noninvasive means of detecting it. Basic laboratory testing (platelet count, AST, ALT, bilirubin, GGT, INR) and standard imaging (conventional ultrasound (US), computed tomography (CT) or magnetic resonance imaging (MRI)) are insensitive to liver congestion and early liver fibrosis in these patients (8). Percutaneous core needle liver biopsy, while the current standard of care, is not an ideal surveillance tool as the core sample may falsely under- or over-estimate the degree of fibrosis given the significant heterogeneity that often exists. Liver biopsy is also invasive and carries a small but real risk of bleeding, particularly in patients who require anti-coagulation.

Ultrasound shear wave elastography (SWE), based on the measurement of tissue shear wave speed, provides a non-invasive measure of liver stiffness and is an extremely promising technology to monitor the congestion and early fibrosis that precedes overt FALD. The utility of ultrasound SWE in assessing liver fibrosis has been well-documented (9, 10) and image-guided ultrasound SWE has been used in TCPC patients to demonstrate that liver stiffness correlates with hepatic congestion (as determined by elevated central venous pressures) and hepatic fibrosis (as determined by liver biopsy) (11-13). MRI-elastography may be of even greater utility as it allows sampling over a much larger region of the liver (thus, minimizing sampling error) and may potentially allow differentiation of stiffness due to fibrosis versus congestion, a feature which may be particularly useful in the evaluation of Fontan patients and in determining the best approach to targeted therapy in this population (14).

3.1.3 FALD and FUEL Extension Study

The FUEL Extension trial is an NHLBI-sponsored study that will assess the efficacy of safety and efficacy of udenafil, a phosphodiesterase-5 inhibitor (PDE-5i) that causes relaxation and decongestion of the pulmonary and systemic venous vasculature, to improve Fontan cardiac function, peripheral endothelial function, and exercise performance in adolescents who have undergone TCPC. By partnering with the FUEL Extension trial, we will have the unique opportunity to 1) measure liver stiffness across a large cross-section of children and adolescents after TCPC; 2) assess how liver stiffness responds to vasodilator therapy determine; 3) determine if liver stiffness correlates with important functional outcomes; and 4) determine the relationship between biomarkers of heart failure and liver fibrosis and liver stiffness. Currently, PDE-5i therapy after the Fontan is reserved for those patients who have clinically symptomatic heart failure. However, a significant and sustained reduction in liver stiffness with PDE-5i therapy would suggest that earlier treatment might reduce the incidence, severity and rate of progression of FALD. This has important implications for a population in whom the rate of liver fibrosis is a critical determinant of overall long-term health.

3.2 Rationale for the Study and Study Outcomes

3.2.1 Study Rationale

While there have been many small studies that have used SWE to evaluate the degree of liver stiffness in patients who have undergone TCPC, there has not been a large-scale evaluation that defines “normal” in this population or seeks to correlate liver stiffness with functional outcome. Similarly, the impact of treatment with pulmonary vasodilators, medications that should lower systemic venous pressure, has not been evaluated. The FUEL Extension trial presents a unique opportunity to measure liver stiffness in those with TCPC, to evaluate the impact of udenafil on liver stiffness, to correlate liver stiffness with functional outcomes, and to gain valuable insight into the relationship between liver stiffness and biomarkers of heart failure and fibrosis.

[figure not shown]
3.2.2 Rationale for Study Outcomes

3.2.2.1 The use of ultrasound SWE to evaluate liver fibrosis

Ultrasound SWE uses one or more acoustic radiation force impulses (ARFI) or “push pulses” to generate shear waves in the tissue of interest. These shear waves can be tracked and their speed measured, with increasing tissue stiffness associated with increasing tissue shear wave speed. Shear wave speed can be mathematically converted to both shear and Young’s moduli (in kPa), mechanical properties related to tissue rigidity and elasticity. There are two major forms of ultrasound SWE – “point” and “2D”. Point ultrasound SWE provides a very focal estimate of liver stiffness using a small region-of-interest, while 2D ultrasound SWE provides a regional color parameteric map (elastogram) of image stiffness and allows measurement over a much larger area of the liver.

[figure not shown]
We have demonstrated excellent inter- and intra-observer reproducibility of ultrasound SWE measurements in soft and hard tissue-mimicking elasticity phantoms using two different US systems (Supersonic Imagine and Siemens Medical Solutions USA) and five different US transducers. Coefficients of variation between various combinations of US systems, transducers, phantoms, and phantom depths were low, ranging from 0.5-6.8%, and inter-operator agreement (four operators) was near-perfect (ICCs ≥ 0.99) (15). We also have explored the *in vivo* relationship between liver shear wave speed and histologic fibrosis and observed significant positive correlations between liver shear wave speed and histologic fibrosis using point and 2D ultrasound SWE (Siemens Acuson S3000) ($r = 0.68$ and $r = 0.73$; p -values <0.0001) ([Figure 2](#)).

Figure 2: Box plot showing increasing liver shear wave speed measurements with increasing parenchymal fibrosis.

Receiver operating characteristic (ROC) areas under the curve for discriminating Ishak fibrosis scores “0-2” (no/mild fibrosis) from “3-6” (moderate/severe fibrosis) were 0.84 and 0.86 for point and 2D ultrasound SWE, respectively. In a recent prospective longitudinal observation study, we have shown that children with single ventricle congenital heart disease experience marked liver stiffening immediately after the TCPC. Five subjects returned at a mean of 185 ± 28 days, and mean liver stiffness remained elevated above baseline but with a variable response between patients when comparing the change in stiffness from early (2.5 and 7.5 days post-op) to late (6 month post-op) time points, which may reflect individual differences in cardiovascular performance or functional reserve (Figure 3).

Figure 3: Individual profile plots from subjects undergoing stage 3 Fontan palliation

[figure not shown]
These plots show changes in liver shear wave speed (stiffness) over time (follow #1 = 2.5 days post-op, follow-up #2 = 7.5 days post-op, and follow-up #3 = 185 days post-Fontan).

